10.4. Secondary Analysis

10.4.1. Paresthesia coverage

Hypothesis:

The non-awake is comparable to the awake method in the proportion of the painful regions covered by paresthesia

Metrics:

Paresthesia overlap percentage

Extraneous paresthesia percentage

The regions marked on the Pain Location Form and Paresthesia Coverage form will be categorized as overlapping, uncovered pain, excess paresthesia, or none (see Table 3; Alo, Yland, Redko, Feler, & Naumann, 1999).

$$paresthesia\ overlap\ percentage = \frac{N_O}{N_U+N_O} \cdot 100$$

$$extraneous\ paresthesia\ percentage = \frac{N_E}{N_O+N_E} \cdot 100$$

Statistical Tests:

Test for normality (such as Jarque-Bera)

Unpaired, two-sided Student’s t-tests (normally distributed continuous data) or Mann-Whitney rank sums test (skewed continuous data)

Significance at $\alpha < 0.05$, with no adjustment for the multiple comparisons

		Paresthesia Coverage Form	
		Marked	Unmarked
Pain Location Form	Marked	Overlap N_O	Uncovered N_U
	Blank	Excess N_E	None N_N

Table 3: Pain-Paresthesia Comparison Categories

10.5. Additional Analysis

Summary statistics will be calculated for additional data. Post-hoc analysis may be done based on findings.

10.6. Data Sets

All patients who complete the 6 week follow-up appointment and questionnaires will be included in the analysis.

Patients with missing baseline values will be excluded from the analysis. Missing data pertaining to adverse events will not be imputed.

11. Withdrawal of Patients from Study

Withdrawal is defined as a patient’s termination of participation from a clinical study. Patients may be discontinued from the study at any time. The reason for discontinuation will be recorded

on the Exit and Withdrawal form. Discontinued patients may not be replaced in the study. Prior to discontinuing a patient, every effort should be made to contact the patient in an effort either to get the patient back into compliance with the protocol, or to obtain as much follow-up data as possible. Reasons for discontinuation include, but are not necessarily limited to:

- Voluntary withdrawal by the patient;
- Patient is Lost to Follow-up: Patient will be considered “lost to follow-up” after a minimum of 2 documented phone calls by personnel at the investigational center to the patient or emergency contact and a certified letter was sent to the last known address.
- Investigator may discontinue the patient’s participation in the study for reasons including but not limited to: patient noncompliance, surgical revision not appropriate, unwillingness or inability to cooperate with study requirements (therapy regimen, follow-up visits, etc.).

12. Modification of Protocol

Any amendments to this protocol must be prepared by the Coordinating Investigator and approved by the appropriate regulatory agencies and the local authority (IRB) before implementation by the Investigator.

13. Discontinuation of Study

The Clinical Coordinating Investigator reserves the right to discontinue any study at any time for administrative reasons, such as but not limited to, a decision to discontinue further clinical Investigations with the devices, improper conduct of the study by the Investigator, inability to obtain the number of patients required by the protocol, etc.

If the study is prematurely terminated or suspended, it is the responsibility of the investigator to promptly inform the patients and assure appropriate therapy and follow-up. The Investigator must also adhere to local IRB requirements and reporting of study termination or discontinuation.

14. References

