7.10. Follow-up Visits

Patients will report to the office at the specified intervals below. Under the guidance of the Investigative team at each visit, SJM field representatives may assist with programming of the patient's device as needed during the course of the study.

Missed visits and visits that occur outside of the specified time windows will be documented as protocol deviations.

7.10.1. 6 Week Visit

Patients will complete additional follow-up visits at 6 weeks for continued monitoring of the safety and efficacy of the therapy. All programming data will be captured on the appropriate case report form.

A map of paresthesia coverage is collected along with programming parameters, lead impedance, and device data. Any changes in medications will be recorded.

Pain metrics to be collected are patient reported pain relief, NRS, and SF-MPQ. Quality of Life (EQ-5D) will also be assessed.

7.10.2. 24 Week Visit

Patients will complete additional follow-up visits at 24 weeks for continued monitoring of the safety and efficacy of the therapy. All programming data will be captured on the appropriate case report form.

A map of paresthesia coverage is collected along with final programming parameters, lead impedance, and device data. Any changes in medications will be recorded.

Pain metrics to be collected are patient-reported pain relief, NRS, and SF-MPQ. Quality of Life (EQ-5D) will also be assessed.

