7.11.2. Adverse Events

Adverse events will be collected according to the section below. Outcomes will be in percentage of patients experiencing events and total number of events, and will be stratified by severity, type, and resolution.

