10.1. Statistical Plan

The study design for this investigation is a post-market, prospective, multicenter, parallel design, non-blinded study with primary analysis at 24 weeks. The primary objective in this study is to demonstrate the effectiveness and safety of the non-awake procedure compared to the awake procedure.

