10.3.2. Number of adverse events

Hypothesis:

The non-awake is comparable to the awake method in the number of adverse events.

Metrics:

Rate of adverse events (percentage of patients with an adverse event)

Statistical Tests:

Chi-square or Fisher's exact test as appropriate based on the number of adverse events
Significance at $\alpha < 0.05$, with no adjustment for the multiple comparisons

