10.3.3. Procedure Time

Hypothesis:

The non-awake is comparable to the awake method in the number of revisions

Metrics:

Rate of revisions (percentage of patients with a revision)

Statistical Tests:

Chi-square or Fisher's exact test as appropriate based on the number of adverse events
Significance at $\alpha < 0.05$, with no adjustment for the multiple comparisons.

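### Section 10.6 ties the primary comparisons to 6-week completion, so implanted patients with recorded procedure times and adverse events can be left out of them

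*Combined protocol and SAP*

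**What the plan says.** Section 10.6 (Data Sets) holds three rules. The first defines who is analysed: "All patients who complete the 6 week follow-up appointment and questionnaires will be included in the analysis". The second removes patients: "Patients with missing baseline values will be excluded from the analysis". The third concerns safety data: "Missing data pertaining to adverse events will not be imputed". The section speaks of a single analysis and does not separate primary, secondary and safety comparisons. No all-implanted, intention-to-treat or safety set is defined anywhere in the document.

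The primary metrics are the procedure-time measures (10.3.1), "Rate of adverse events (percentage of patients with an adverse event") in 10.3.2 and "Rate of revisions (percentage of patients with a revision") in 10.3.3, a section that carries the heading Procedure Time but concerns revisions. None states its denominator. Section 7.11.2 describes the adverse-event outcome as "Outcomes will be in percentage of patients experiencing events and total number of events", also without a completer condition.

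Section 10.1 describes a "non-blinded study with primary analysis at 24 weeks". Section 7.10 foresees irregular attendance: "Missed visits and visits that occur outside of the specified time windows will be documented as protocol deviations". Under 7.7, a patient whose device is fully explanted and who cannot be re-implanted leaves the study. Section 11 lists unsuitability for surgical revision among the reasons for discontinuation, and asks sites to collect as much follow-up data as they can from patients who are leaving.

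**The concern.** A condition that can be met only weeks after surgery decides who enters comparisons whose data are largely complete by then. Three kinds of implanted patient can be left out, although their data remain on the case report forms:

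- **Early exits.** Examples are complete explant without re-implantation (7.7) and unsuitability for revision (Section 11). The route is narrow, but it makes inclusion in the safety comparison depend on a safety outcome.
- **Patients still in follow-up** who miss the 6-week visit or leave its questionnaires incomplete, even if they attend at 24 weeks, when the primary analysis takes place.
- **Patients with missing baseline values**, although the tests in 10.3 are unadjusted and use no baseline value.

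The condition does not secure full follow-up either, since a patient who exits just after 6 weeks is kept.

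Sections 10.3.2 and 10.3.3 hypothesise comparability, and 10.2 rules out a formal non-inferiority margin. The conclusion will therefore rest on the estimated rates, and with about 25 patients per arm one or two patients move those rates visibly. Each site uses only one technique (Section 6), so differences in attendance between sites become differences between arms.

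**Working it through.** **Timing.** Inputs: activation about 14 to 21 days after implantation (7.8); 6-week visit at 42 ± 7 days after activation (Table 1); procedure-related events defined within 30 days of the procedure (8.1).

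- Earliest usual visit day after implantation: 14 + 42 − 7 = 49. Latest: 21 + 42 + 7 = 70.
- If the device is activated at discharge, which Table 1 allows for: 0 + 42 − 7 = day 35.

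In every case the visit comes after the 30-day window has closed, and long after skin-to-skin time was fixed at the last suture (7.11.1).

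**Follow-up of a patient kept at 6 weeks.** Measured from activation, 42/168 = 25%, which leaves 126 days unobserved. Adverse events are collected from implantation (8.3); on that clock the share is 56/182 = 31% (activation at day 14) to 63/189 = 33% (day 21).

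**Adverse-event rates.** The planned minimum is 50 patients at 1:1 (10.2), or 25 per arm. The documents give no exit or missed-visit rate, so all event and exclusion counts below are assumptions. Suppose both arms truly have 6/25 = 24.0%, and patients with events are left out of one arm only:

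| Event patients left out | Observed in that arm | False difference (points) | Two-sided Fisher p |
|---|---|---|---|
| 1 | 5/24 = 20.8% | 3.2 | 1.00 |
| 2 | 4/23 = 17.4% | 6.6 | 0.73 |
| 3 | 3/22 = 13.6% | 10.4 | 0.47 |

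- A real difference can shrink. True rates of 9/25 and 6/25 differ by 36.0 − 24.0 = 12.0 points (p = 0.54). Leaving two event patients out of the worse arm gives 7/23 against 6/25, or 30.4 − 24.0 = 6.4 points (p = 0.75).
- The rate can also rise: leaving out two event-free patients gives 6/23 = 26.1%.
- At the cap of 30 per arm (Section 6), leaving out two event patients moves 6/30 = 20.0% to 4/28 = 14.3%.

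**Revisions.** Assume 25 patients, of whom 5 are revised and 2 others are explanted early without revision.

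- Completer set: 5/23 = 21.7%.
- All implanted, explant scored as no revision: 5/25 = 20.0%.
- All implanted, revision or explant: 7/25 = 28.0%.

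If instead two of the five revised patients exit early, the completer set gives 3/23 = 13.0%. The direction depends on who leaves and on whether an explant counts as a revision, which the documents do not say.

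**Procedure time.** Losing 2 of 25 patients raises that arm's standard error by √(25/23) − 1 = 4.3%.

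**The case against.** The strongest reply is that 10.6 never says that only completers are analysed. Its first sentence is an inclusion statement, whereas its second uses exclusion wording, so the authors had that wording at hand. Section 7.11.2 sets no completer condition, and 8.2 and 8.3 require all device- or procedure-related and all serious events to be recorded from implantation. This makes the text partly ambiguous, but it does not clear it. As the sole population statement, the sentence has no function unless it defines who is analysed, and the adverse-event rule beside it shows that the section is meant to govern safety data.

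The second reply is that the routes are narrow. Coordinators check questionnaires for completeness (7.12), and omissions on the case report forms generate queries (9.3). That limits losses from incomplete forms, but not from missed visits or early exits. Under 7.7, migrated leads can be repositioned and re-implantation can follow an infection, so a revised patient ordinarily stays in the study. Table 2's infection rates imply about 25 × 4.5% = 1.1 and 25 × 6.0% = 1.5 patients per arm, and only some of these would be explanted for good before week 6. Losing two or three event patients from one arm would therefore probably need other causes as well. This part stands, and it is why the size cannot be fixed.

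The third reply is that no test result changes and the direction between arms is undetermined. Both are true of the cases above. They limit the severity, but they do not justify discarding recorded primary data.

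**Conclusion.** The concern holds. Followed as written, 10.6 removes recorded procedure times, adverse events and revisions from the primary comparisons for reasons those comparisons do not need, and in the early-explant case for a reason tied to outcome. Adverse-event rates are understated when the patients left out are those with events. The direction is undetermined for the between-arm contrast and for revisions.

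The size is unknown. Under the assumed one-arm losses of one to three event patients per 25, the false difference runs from 3.2 to 10.4 points without reaching significance. For procedure time, the illustrated cost is a small loss of precision. Room to enrol up to 30 per arm softens that loss but does not remove selection bias. The conclusion rests on reading 10.6 as the population for all analyses, which is the natural reading but not an explicit one. This should be fixed; it does not invalidate the trial.

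**What to change.** Amend 10.6 to define a set for each endpoint:

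1. **Procedure time, adverse events and revisions:** every patient in whom study implantation was started, without requiring the 6-week visit, its questionnaires or baseline values. State how times from an abandoned procedure are handled. Count all events recorded up to exit or 24 weeks, impute none after exit (as 10.6 already provides), and report length of follow-up by arm. As a bound, count each early exit without a recorded event as an event; with two such exits, 6/25 = 24.0% becomes 8/25 = 32.0%.
2. **Explants:** state whether an explant counts as a revision, or report explants separately together with a combined revision-or-explant outcome, so that an early explant is not scored as event-free.
3. **Paresthesia coverage:** all patients with the pain and paresthesia maps that the calculation needs.
4. **Reporting:** number, timing and reason of exits and missed visits up to week 6, by arm, with the 6-week-completer set kept as a sensitivity analysis.

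Item 1 is the essential change; the bound and item 2 support it. The cost is an amendment with the approvals required by Section 12. No new visits are needed, and the Surgery, Adverse Event and Exit and Withdrawal forms are the expected sources. The forms themselves are not in the reviewed document, and 7.10.3 calls for the Additional Surgery form at revision or replacement, not at explant alone, so the sponsor should confirm that explants are captured. Reported adverse-event rates may become less favourable.

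### The 24-week adverse-event and revision percentages count patients lost between weeks 6 and 24 as event-free, which biases late-event rates downward by a modest amount

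*Combined protocol and SAP*

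**What the plan says.** All references are to the combined protocol and SAP.

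- **Time point.** Section 10.1 describes a "non-blinded study with primary analysis at 24 weeks". Sections 10.3.2 and 10.3.3 name no time point of their own.
- **Analysis set.** Section 10.6: "All patients who complete the 6 week follow-up appointment and questionnaires will be included in the analysis". The same section adds: "Patients with missing baseline values will be excluded from the analysis".
- **Missing data.** Section 10.6: "Missing data pertaining to adverse events will not be imputed". Nothing is said about missing revision data or partial follow-up.
- **Metrics.** Section 10.3.2 defines its outcome as "Rate of adverse events (percentage of patients with an adverse event" and section 10.3.3 as "Rate of revisions (percentage of patients with a revision", in each case a plain proportion.
- **Tests.** Both sections use chi-square or Fisher's test at the 5% level. There is no person-time, time-to-event or sensitivity analysis.
- **Loss.** Section 11 defines loss to follow-up, allows withdrawal at any time and says that discontinued patients may not be replaced. Section 10.2 assumes no screen failures and gives no rate of loss after implantation.

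**The concern.** Membership of the analysis set is settled at week 6, but the outcome is read at week 24. A patient who reaches week 6, has no event and is lost at week 8 has an unknown 24-week status. Section 10.6 keeps that patient in the analysis. With a plain percentage and no imputation or censoring, the patient can add to the denominator but not to the numerator. The 16 unobserved weeks are treated as event-free.

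Two things are at stake. First, the reported rates understate late events. Second, arm is fixed by site (section 6), so if retention differs between sites it differs between arms, and the error need not cancel. Even with equal loss, the arm with more events loses more of them, which shrinks the difference. The stated hypotheses for adverse events and revisions are of comparability, so that shrinkage runs in the direction of the claim.

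**Working it through.** **No figure in the plan to reproduce.** The plan gives no loss rate and no rate adjusted for loss. The only documented inputs are the revision rates in Table 2 of section 10.2 (30% awake, 15% non-awake) and 25 patients per arm (50 enrolled 1:1). The loss fractions and event timing below are assumptions.

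**Step 1. Which events can be missed.** Section 8.1 limits procedure-related adverse events to 30 days after the procedure. Activation is about 2 to 3 weeks after implantation (section 7.8), and the week-6 visit is 42 ± 7 days after activation (Table 1).

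- Earliest week-6 visit: 14 + 35 = 49 days after implantation. Latest: 21 + 49 = 70 days.
- Even if the device were activated on the day of implantation, the earliest visit in window would be day 35, which is after day 30.

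Loss after week 6 therefore cannot hide an adverse event related to the index procedure. It can hide revisions, adverse events of revision procedures, device-related adverse events and other serious adverse events.

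**Step 2. Expected rate with lost patients counted as event-free.** Let p be the true 24-week rate, L the fraction lost and u the week of loss, uniform on 6 to 24. With a constant hazard, λ = −ln(1 − p)/24.

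- Mean risk up to loss: m = 1 − (e^(−6λ) − e^(−24λ))/(18λ)
- Expected crude rate: (1 − L)p + Lm = p − L(p − m)

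For p = 30%: λ = 0.01486, and m = 1 − (0.9147 − 0.7000)/0.2675 = 19.7%. The shortfall is 10.26 points × L.

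For p = 15%: λ = 0.00677, and m = 1 − (0.9602 − 0.8500)/0.1219 = 9.6%. The shortfall is 5.40 points × L.

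| Loss after week 6 | True 30% | True 15% | Difference, equal loss (true 15.0) |
|---|---|---|---|
| 10% | 29.0% | 14.5% | 14.5 |
| 20% | 27.9% | 13.9% | 14.0 |
| 30% | 26.9% | 13.4% | 13.5 |

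**Step 3. Unequal loss.** If both arms truly have 30% and only one loses 30% of its patients, the spurious difference is 0.30 × 10.26 = 3.1 points.

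**Step 4. Sensitivity to event timing.** The constant hazard puts 8.5 of the 30 points before week 6, or about 28% of events. Suppose instead that half fall before week 6, leaving 15 points at risk of being missed.

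- Late events even over weeks 6 to 24, loss as in step 2: half of the late events in lost patients are missed. The rate is 30 − L × 7.5, or 29.3% at 10% loss and 28.5% at 20%.
- All loss just after week 6: all late events in lost patients are missed. The rate is 30 − L × 15, or 28.5% and 27.0%.
- As the previous case, but lost patients have twice the late risk of retained patients: 27.3% and 25.0%.

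**Step 5. Yardstick.** The standard error of a difference of 30% against 15% with 25 per arm is √(0.30 × 0.70/25 + 0.15 × 0.85/25) = √0.0135 = 11.6 points. One patient of unknown status moves an arm's rate by up to 1/25 = 4.0 points, or 1/30 = 3.3 points at the cap of 30 per arm.

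**The case against.** **The plan is only silent, and any handling would be biased.** A reader might infer that lost patients are either counted as event-free or dropped, and that both choices give a wrong rate. The documents do not support this.

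- Dropping a week-6 completer contradicts section 10.6, which includes that patient.
- Dropping every lost patient, events and all, gives an unbiased 30.0% when loss is unrelated to risk.
- An upward bias (31.5%, 33.3% and 35.5% at 10%, 20% and 30% loss, under the assumptions of step 2) arises only if lost patients without events are removed while lost patients with events are kept. No section states that rule.

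**The missing-data sentence is narrow.** It names adverse events only and could be read as referring to incomplete event records. This is right. For revisions, the event-free count follows from the inclusion rule and the plain percentage, not from that sentence.

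**Differential loss is not documented.** Section 11 sets one definition for all sites (two documented calls and a certified letter) and asks for every effort to obtain follow-up data before discontinuation. That should limit loss. But each centre does its own tracing, so unequal loss by arm is possible. It is not established.

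**The effect is small.** This stands. At 25 per arm, a bias of 1 to 3 points is well inside sampling error.

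**Kaplan-Meier has its own assumption.** Censoring must be unrelated to risk. Section 7.7 ends participation after complete explant without re-implantation, and section 11 lets the investigator discontinue a patient for whom revision surgery is judged unsuitable. Exit can therefore be tied to outcome. This also stands, and it is why bounds are needed beside the estimate.

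**Conclusion.** The point holds in a limited form. The stated rules, taken together, count patients lost between weeks 6 and 24 as event-free. The 24-week rates of revisions and late adverse events are then understated whenever a late event is missed. A true 30% becomes 29.0%, 27.9% or 26.9% at 10%, 20% or 30% loss, assuming a constant hazard and uniform loss. Other event timing with loss unrelated to risk gives 28.5% to 29.3% at 10% loss and 27.0% to 28.5% at 20%. With doubled late risk in lost patients, the figures are 27.3% and 25.0%.

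The real loss rate is not in the documents, so the actual size is unknown. It is modest against a standard error of about 12 points. The comparison of adverse events related to the index procedure is untouched. This is a worthwhile low-cost improvement and does not undermine the trial. Patients who leave before week 6, whom section 10.6 excludes altogether, are a separate matter.

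**What to change.** In sections 10.3.2 and 10.3.3:

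1. Report for each arm the proportion with an event by week 24, estimated by Kaplan-Meier with censoring at last contact, and give the arm difference with its confidence interval.
2. Keep the crude percentages and the planned chi-square or Fisher test beside it. A change to the log-rank test is not needed. It compares whole curves and not the week-24 proportion, and Fisher's test suits small event counts.
3. Add a best/worst-case analysis in which patients of unknown 24-week status are set to no event and to event, including the two mixed cases by arm. Report the number of such patients per arm.

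In section 10.6, state that these rules apply to revisions as well as adverse events.

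**Cost.** SAP wording and a little programming, with no extra patients. The estimate assumes that censoring is unrelated to risk, and the bounds show how much rests on that. The case report forms are not in the document, so the sponsor must confirm that the adverse event, additional surgery and exit forms record dates. If they do not, a date field has to be added.

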7.7. Postoperative Management and Instruction

The physician will provide normal standard of care after implantation of the system, including standard post-operative monitoring. Instructions for wound care and monitoring will be provided to the patient by the implanting physician. Patients will be informed to report any adverse events or changes in medication to study personnel. Patients will be informed not to manipulate the leads after implantation because tissue erosion may occur. The patient will be sent home for a 2-3 week recovery period to let any swelling and/or post-operative pain subside prior to activation of SCS system, unless otherwise

determined by the installing investigator. During this time, the device may not be activated and the patient may not be provided with the Patient Programmer. Prophylactic antibiotic therapy may be instituted at the discretion of the Investigator.

If the leads migrate during the study, the implanting physician will examine the area of implantation. The leads can be repositioned or re-implanted if mutually agreed upon by the physician and the patient. The patient and the implanting physician will make the mutual decision about any possible revision of the device based upon what is medically safe, what is desired by the patient, and what is in the patient's best medical interests.

If an infection occurs, standard medical practice suggests that the leads be removed and the patients undergo a standard course of oral antibiotics. Any infection or wound will be given time to heal before any re-implantation is attempted.

If the device is completely explanted from the study patient for any reason and re-implantation is not an option, then the patient will exit the study.

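### The primary revision rate has no definition of a revision and no rule for permanent explant or a needed revision not done, so failures can be dropped or scored revision-free

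*Combined protocol and SAP*

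**What the plan says.** Section 2.3 lists the number of revisions as a primary variable. Section 10.3.3, which is headed Procedure Time but deals with revisions, states the hypothesis as "The non-awake is comparable to the awake method in the number of revisions". Its metric is the "Rate of revisions (percentage of patients with a revision"), compared by chi-square or Fisher's exact test at 5%. Section 10.2 declines to set a non-inferiority margin. No section defines a revision.

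Two rules govern patients whose system fails and is not revised:

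- Section 7.7 is mandatory and covers a system "completely explanted from the study patient for any reason and re-implantation is not an option, then the patient will exit the study".
- Section 11 is permissive: the investigator may discontinue a patient for reasons that include "patient noncompliance, surgical revision not appropriate, unwillingness or inability to cooperate with study requirements".

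On the decision to revise, section 7.7 says: "The patient and the implanting physician will make the mutual decision about any possible revision of the device". Section 3.1 has each investigator use only one of the two methods, and the study is not blinded.

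On who is analysed, section 10.6 says: "All patients who complete the 6 week follow-up appointment and questionnaires will be included in the analysis". It adds: "Missing data pertaining to adverse events will not be imputed". It says nothing comparable for revisions. Section 10.1 puts the primary analysis at 24 weeks. Section 7.10.3 calls for the Additional Surgery form when a revision or replacement is needed and does not mention explant. Appendix A lists that form as completed when needed.

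**The concern.** A system that fails can be revised, removed for good, or left alone because revision is judged unsuitable. Only the first is plainly an event in the primary revision rate. The second requires the patient to leave the study and the third permits it. Unless someone decides otherwise at analysis, the rate then omits patients who may have done worse than those revised.

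The study is exposed to this for two reasons. First, method and investigator are tied together, so a surgeon's or site's tendency to explant or leave alone rather than revise cannot be separated from the method. Second, the hypothesis is one of comparability without a margin, so anything that narrows the observed difference makes the hoped-for reading easier. With no definition, the coding could also be settled after unblinded data have been seen.

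**Working it through.** **1. When does an exit remove a patient, and when does it leave a non-event?** Activation is about 14 to 21 days after implant (section 7.8). The 6-week visit is 42 ± 7 days after activation (Table 1), that is 35 to 49 days. So the visit falls 14 + 35 = 49 to 21 + 49 = 70 days after implant, or about 7 to 10 weeks.

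- Exit before that visit: the patient does not meet section 10.6 and leaves both numerator and denominator.
- Exit after it: the patient stays in the denominator and, read literally, has no revision unless one was done earlier.

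**2. The plan's own figure.** Section 10.2 gives a minimum of 50 patients, 1:1, so 25 per arm. It cannot be reproduced, because power, the SD of procedure time and the endpoint simulated are not stated. The point does not depend on it; 25 per arm is used only to set the scale. One patient is 1/25 = 4 percentage points.

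**3. Effect of one patient (two-sided Fisher; illustrative counts, non-awake versus awake).**

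| How one of seven awake failures is handled | Counts | p |
|---|---|---|
| Counted as an event | 1/25 vs 7/25 | 0.049 |
| Exits after week 6, scored as a non-event | 1/25 vs 6/25 | 0.098 |
| Exits before week 6, excluded | 1/25 vs 6/24 | 0.049 |

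With two exits among nine awake failures, 2/25 versus 9/25 (p = 0.037) becomes 2/25 versus 7/25 (p = 0.138) as non-events, or 2/25 versus 7/23 (p = 0.068) if excluded. So exit timing and coding can change the result.

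**4. Effect on the rates.** Table 2 gives revision for device failure as p = 15% (non-awake) and 30% (awake). Treat these, for illustration, as the true failure rates. Let f be the share of failures that exit unrevised. The documents give no f, so the values below are assumptions.

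- Exits scored as non-events: observed rate = p(1 − f).
- Exits excluded: observed rate = p(1 − f) / (1 − pf).

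For example, awake with f = 20%: 0.30 × 0.80 = 24.0%, or 0.24 / (1 − 0.06) = 25.5%.

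| Assumed f, non-awake / awake | Non-events (difference) | Excluded (difference) |
|---|---|---|
| 0 / 0 | 15% vs 30% (15 points) | 15% vs 30% (15 points) |
| 20% / 20% | 12.0% vs 24.0% (12.0) | 12.4% vs 25.5% (13.2) |
| 33% / 33% | 10.05% vs 20.1% (10.05) | 10.6% vs 22.3% (11.7) |
| 0 / 33% | 15% vs 20.1% (5.1) | 15% vs 22.3% (7.3) |
| 33% / 0 | 10.05% vs 30% (19.95) | 10.6% vs 30% (19.4) |

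Both codings lower the observed rate in an arm with exits. Equal shares narrow the difference. Unequal shares can narrow or widen it.

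**The case against.** A reader might infer that the worst placement failures are counted as successes. The documents do not support that, for four reasons.

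- Exits in roughly the first 7 to 10 weeks are excluded under section 10.6, not scored. The p = 0.098 result above needs a late exit.
- A patient may be revised first and explanted or discontinued later, and then has a revision on record. Since the term is undefined, explant surgery could even be read as a revision.
- The exit rule in 7.7 applies to explant for any reason, infection included, so an explant is not necessarily a placement failure.
- Discontinuation under section 11 is allowed, not required, and the phrase about unsuitable revision is not explained.

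Nor do the documents show that permanent explants are to be expected. Table 2's infection rates give 1 − 0.955^25 × 0.94^25 = 93% as the chance of at least one infection in 25 + 25 patients. That is not the chance of a permanent explant: for infection, section 7.7 describes lead removal and healing ahead of any re-implantation. Likewise, one could halve only the awake rate, from 30% to 15%, and make the arms equal. Nothing supports that asymmetry, and the same assumption in both arms gives 7.5% versus 15%. No direction of bias between the methods can be claimed.

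Some of the information is also captured elsewhere. Related and serious adverse events must be recorded (8.2), the adverse event rate is itself primary (10.3.2), and section 11 records the reason for exit and asks for as much follow-up data as possible.

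These objections limit the claim but do not remove it. The adverse event rate is a different endpoint and does not correct the revision rate, and no section links the exit, explant or surgery records to the revision endpoint. That the term could be read to include explant is the ambiguity that needs settling.

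**Conclusion.** The concern holds in a limited form. The plan neither defines a revision nor counts permanent explant, or exit because revision was judged unsuitable, in the primary revision rate. Unless revised earlier, such patients are dropped if they leave before the 6-week visit and, on a literal reading, scored revision-free if they leave after it. The rate can therefore miss device or placement failures.

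The size cannot be determined, because no permanent-explant or exit rate is given. Each affected late exit moves an arm of 25 by 4 points, and in the illustrative counts a single one moves p from 0.049 to 0.098. The direction of any effect on the comparison is also unknown. Equal exit shares favour a finding of comparability, while unequal shares could favour either method. The counts in step 3 and the exit shares in step 4 are assumptions. This should be corrected, as it affects a primary endpoint in a study where method and investigator cannot be separated.

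**What to change.** - **Sections 2.3 and 10.3.3:** define the event as revision, repositioning or replacement; or permanent explant; or study exit because a needed revision was not done. Report each component by arm, show explants for infection separately, and give revision alone as a sensitivity analysis.
- **Section 10.6:** for this endpoint, count events in all implanted patients, whether or not they later exit.
- **Section 7.10.3:** name explant as a trigger for the Additional Surgery form.
- **Section 11:** state that exit because revision was judged unsuitable is recorded as an endpoint event and that follow-up data are still sought. Deleting the phrase would not be enough, because the list of reasons is permissive and not exhaustive.

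The cost is wording in five places. The exit, surgery and adverse event forms already exist, and no visit or procedure is added. The downside is that the composite is broader than placement-related revision, which the component reporting and the sensitivity analysis make visible. Whether a revision or explant is clinically appropriate remains with the investigator; the change concerns only what is recorded and counted.
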